A potential solution to this problem involves dose-reduced SRS to a level which substantially reduces radionecrosis risk without sacrificing the approximately 80-85% six-month local control provided by the present dosing schema, which from RTOG 90-05 has remained 24 Gy for lesions 0-2 cm, 18 Gy for lesions 2.1-3 cm, and 15 Gy for lesions 3-4 cm (Shaw et al., 2000). To maintain a dosing schema less toxic than the RTOG 90-05 regimen while remaining within SRS doses established by Level I evidence to provide local control (Brown et al., 2017), we propose the following dose-reduced SRS protocol for this *Radiosurgery Dose Reduction for Brain Metastases on Immunotherapy* (RADREMI) prospective pilot study: 18 Gy (0-2 cm lesions), 14 Gy (2.1-3 cm lesions), and 12 Gy (3-4 cm lesions) for brain metastases patients receiving at least one immunotherapy agent. These doses are consistent with Level I evidence comparing SRS with whole brain radiation therapy for metastatic brain disease, which revealed that SRS doses of 12-20 Gy were sufficient to provide local control (Brown et al., 2017). For perspective, it is important to remember that RTOG 90-05 was not a dose finding study, but rather a dose tolerance study; subsequent work has established improved local control compared to RTOG 90-05 while using lower doses than the RTOG 90-05 regimen (Shehata et al., 2004; Colaco et al., 2016). Given the efficacy of immunotherapy alone in treating melanoma brain metastases (Tawbi et al., 2018), it is reasonable to hypothesize that a lower SRS dose than the RTOG 90-05 schema will result in a combinatorial effect sufficient to provide local control without resulting in the 20% symptomatic necrosis rate seen with the present dosing schema (Martin et al., 2018).

Summary and Rationale

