In summary, this study seeks to assess the efficacy and safety of radiosurgery dose reduction for brain metastases patients receiving immunotherapy. We hypothesize that: 1. Dose-reduced SRS will reduce the risk of radionecrosis compared to the 16% average rate per patient from the existing concurrent SRS + ICI literature (Skrepnik et al., 2017; Martin et al., 2018) with current SRS dose, and 2. Dose-reduced SRS demonstrates non-inferior efficacy (measured primarily through six-month local tumor control) compared to the 80% local control rate associated with the RTOG 90-05-established SRS dosing parameters. For the purposes of this study, radionecrosis will be defined as clinical symptomatology following SRS requiring steroid utilization and/or operative intervention in combination with imaging features strongly suggesting radionecrosis as demonstrated utilizing routine MRI, MR Perfusion, MR Spectroscopy, and/or PET imaging. Although the definition of concurrent SRS+ICI has varied greatly in the literature, ranging from 2 weeks to 4 months with some studies defining administration within 4 months as concurrent (Anderson et al., 2017; Chen et al., 2018); for the purposes of this study, concurrent therapy will be defined as ICI administered within 30 days of SRS. We also hope to explore SRS radionecrosis rates in multi-agent versus single-agent immunotherapy, as well as in melanoma versus non-melanoma brain metastases. Local control will be defined as a less than 20% increase in tumor size following SRS, as previously described using Response Assessment in Neuro-Oncology (RANO) criteria (Lin et al., 2015).

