14.4 Sample Size

An optimum one-stage design is planned. We specify a historical 6 month symptomatic radiation necrosis rate of 16% and an expected 6 month symptomatic radiation necrosis rate of 5%. Then, to achieve a power of 80% and control the type I error below 10%, a total of 40 patients evaluable for symptomatic radiation necrosis will be enrolled in the study. If at most 4 patients will experience symptomatic radiation necrosis in 6 months, the proposed dose reduction is claimed to be desirable. Otherwise, it is undesirable. We assume that at most 5% of the patients will not be evaluable for symptomatic radiation necrosis, which results in a total sample size of 42. In addition, we will add an interim analysis for the 6 month local control rate. When 20 patients have been enrolled in the study with their local control outcome being available, we will conduct a binomial exact test for the null hypothesis that the proposed method can maintain a 6 month local control rate of at least 75%. If p-value of this binomial test is less than 0.05, we will reject the null hypothesis and terminate this study earlier for futility.

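### Apart from one futility look at 20 patients, local control has no part in the final verdict, although keeping it is half of the stated aim

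*Combined protocol and SAP*

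**What the plan says.** The aim in Section 2 has two parts. Under the proposed solution, the protocol looks for a dose that "substantially reduces radionecrosis risk without sacrificing the approximately 80-85% six-month local control provided by the present dosing schema". The summary that follows says "In summary, this study seeks to assess the efficacy and safety of radiosurgery dose reduction for brain metastases patients receiving immunotherapy" and gives two numbered hypotheses: less radionecrosis than the 16% literature average, and local control at six months that is non-inferior to 80%. No non-inferiority margin is given.

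The final rule in Section 14.4 has one part. With 40 patients evaluable for necrosis, "If at most 4 patients will experience symptomatic radiation necrosis in 6 months, the proposed dose reduction is claimed to be desirable"; any higher count makes it undesirable. Section 14.7 tests necrosis only. Section 14.8 gives local control a Kaplan-Meier estimate with a 95% confidence interval, without a threshold, a margin or a link to the verdict.

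Local control does enter Section 14.4 once. "When 20 patients have been enrolled in the study with their local control outcome being available", an exact binomial test is made of the null hypothesis that 6-month local control is at least 75%, and the study stops for futility if p is below 0.05. The test is not repeated later.

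**The concern.** Desirable is a verdict on the dose reduction as a whole, so a reader will take it to cover both halves of the aim. After the interim look, the local control results of the remaining patients cannot alter that verdict, however poor they are. The plan treats rejection of a 75% rate at 20 patients as grounds to end the study, yet the same rejection at 40 would leave the conclusion unchanged. At stake is a headline that endorses the reduced dose when the trial's own data contradict the 75% standard it set.

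**Working it through.** **Inputs.** From Section 14.4: 40 evaluable patients, at most 4 necrosis events, historical rate 16%, expected rate 5%, interim at 20 patients with a 75% null and p < 0.05. From Section 2: 57% local control with multi-agent checkpoint inhibition alone, and 80% as the reference for radiosurgery.

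**Assumptions.** True necrosis is 5%. Local control and necrosis are independent. The interim test is one-sided; Section 14.4 does not state this, but the null implies it. All 40 patients, including the 20 at the interim, are evaluable for local control. The 65% scenario is an assumption of this review.

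**The plan's own necrosis rule.** With X ~ Bin(40, p), the type I error is P(X ≤ r | 0.16) and the power is P(X ≤ r | 0.05):

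- r = 4 (as printed): type I error 21.1%, power 95.2%
- r = 3: type I error 9.84%, power 86.2%
- r = 2: type I error 3.45%, power 67.7%

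The printed cut-off does not meet the stated type I error below 10%; 3 or fewer does. Section 14.7 tests at 5%, which needs 2 or fewer. That discrepancy is a separate matter, but results are shown for all three cut-offs because the final rule could settle on any of them.

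**Interim.** At 75%, P(X ≤ 11 | 20) = 0.0409 and P(X ≤ 12 | 20) = 0.1018, so the study stops at 11 or fewer controlled. The chance of stopping is 0.94 at a true local control of 40%, 0.75 at 50%, 0.51 at 57% and 0.24 at 65%. Read two-sided, it would stop only at 10 or fewer, and the chance at 57% would fall to 0.34.

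**Same test on 40.** At 75%, P(X ≤ 24 | 40) = 0.0262 and P(X ≤ 25 | 40) = 0.0544, so the test rejects at 24 or fewer and passes at 25 or more.

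**Chance of the claim.**

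- As written: P(X₁ ≥ 12) × P(necrosis ≤ r), with X₁ ~ Bin(20, LC).
- With a final check: [Σ over x = 12 to 20 of P(X₁ = x) × P(X₂ ≥ 25 − x)] × P(necrosis ≤ r), with X₂ ~ Bin(20, LC).

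For example, at 57% and r = 4: 0.4864 × 0.9520 = 0.463 as written, and 0.2511 × 0.9520 = 0.239 with the check.

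| True local control | Passes interim | Passes both | Claim, r = 4 | Claim, r = 3 | Claim, r = 2 |
|---|---|---|---|---|---|
| 57% | 0.486 | 0.251 | 0.46 → 0.24 | 0.42 → 0.22 | 0.33 → 0.17 |
| 65% | 0.762 | 0.625 | 0.73 → 0.60 | 0.66 → 0.54 | 0.52 → 0.42 |
| 75% | 0.959 | 0.945 | 0.913 → 0.900 | 0.83 → 0.81 | 0.65 → 0.64 |
| 80% | 0.990 | 0.988 | 0.942 → 0.941 | 0.85 → 0.85 | 0.67 → 0.67 |

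**Dependence.** Under any dependence between the endpoints, the as-written probability for r = 4 lies between P(pass interim) + 0.952 − 1 and the smaller of the two probabilities. That gives 0.44 to 0.49 at 57% and 0.71 to 0.76 at 65%, so independence is not what drives these as-written figures.

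**The case against.** This is a single-arm pilot whose only primary endpoint is 6-month symptomatic necrosis. Building the verdict on the primary endpoint, with efficacy as a futility gate and a secondary estimate, is a conventional structure. Local control will be reported with an interval, so a poor result would be visible beside the label. Section 17 also provides monthly review and allows early closure on risk or benefit. All of this is correct, and it limits the point to the rule for the label. It does not remove the point, because Section 2 makes non-inferior local control a numbered hypothesis and no final rule addresses it.

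Three stronger readings are tempting, and the documents support none of them.

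- A reader might infer that the plan ignores local control altogether. It does not: the interim look catches gross failure.
- A reader might put the whole 0.46 or 0.73 down to the missing final criterion. Those figures are the interim pass probability times a constant, so they mostly measure the sensitivity of the interim. Only the reductions belong here.
- A reader might argue that the rule is easiest to meet when the dose does least. Section 2 offers lower necrosis at lower dose as a hypothesis, and the calculation holds necrosis at 5% throughout, so it does not model that mechanism.

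The 57% scenario is also severe. It is a rate without radiosurgery, so it supposes that the reduced dose adds nothing to multi-agent therapy.

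**Conclusion.** The point holds as a gap between the stated aim and the final rule. Local control that fails the plan's own 75% test in the full sample would still be labelled desirable. Under the stated assumptions, closing the gap lowers the chance of that label at a true 57% by 0.22 with the printed cut-off (0.20 with 3 or fewer events, 0.16 with 2 or fewer), and at 65% by 0.13 (0.12 and 0.10), from the rounded table entries.

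It would be wrong to infer that a final check establishes that local control was kept. Passing at 25 of 40 is an observed 62.5%, and counts of 25 to 29, all below 75%, would still pass. Nor can this sample show tight non-inferiority: an exact one-sided 5% test that local control exceeds 75% needs 35 of 40 and has power 0.16 at a true 80%.

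**What to change.** In Section 14.4, claim the dose reduction desirable only if the necrosis limit is met and the one-sided exact test of 6-month local control of at least 75%, repeated on all patients evaluable for 6-month local control, does not reject at 0.05.

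- **Denominator.** The 40 in Section 14.4 are those evaluable for necrosis, so local control needs its own count. If 40 are evaluable, the requirement is at least 25 controlled; recompute the cut-off for the actual number.
- **Deaths and censoring before 6 months.** Treat them as at the interim. Section 14.4 does not spell out that rule, so write it once for both tests.
- **Necrosis passes, local control fails.** Report lower necrosis, local control not maintained.
- **Both pass.** Report the local control estimate and its 95% interval beside the 80% reference, and state that this is a minimum safeguard and not evidence of non-inferiority.

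The cost is protocol and SAP wording and one further exact test on data already collected, with no more patients. With the printed necrosis cut-off, the chance of the claim falls from 0.913 to 0.900 at a true local control of exactly 75% and is essentially unchanged at 80% (0.942 to 0.941). A stricter count is possible but costs more: requiring 30 of 40 cuts the claim to 0.014 at 57%, but to 0.80 at 80%.

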4.2 Secondary Outcome Measure

1. 6 month local control, defined as a 6-month rate of any new, recurrent or progressing (as defined by RANO criteria) tumor within the planning target volume compared to pre-SRS on any post-treatment MRI by 6 months. Follow-up MRIs will be fused with the planning scan for this assessment.
2. 6 month radiographic radiation necrosis, defined as brain imaging findings (MRI, MR Perfusion, MR Spectroscopy, and/or PET) consistent with radiation necrosis.
3. 12 month local control
4. 12 month symptomatic radiation necrosis
5. 12 month radiographic radiation necrosis
6. Evaluation of 12 month local control rate by SRS modality (Gamma Knife versus Linear Accelerator)
7. Evaluation of 12 month local control rate by single agent versus multi-agent ICI
8. Evaluation of 12 month local control rate by melanoma versus non-melanoma brain metastases
9. Evaluation of 12 month symptomatic radiation necrosis rate by SRS modality (Gamma Knife versus Linear Accelerator)
10. Evaluation of 12 month symptomatic radiation necrosis rate by single agent versus multi-agent ICI
11. Evaluation of 12 month symptomatic radiation necrosis rate by melanoma versus non-melanoma brain metastases

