8.5 One Month Follow-Up

A detailed medical history, toxicity assessment and physical examination including vital signs along with a brain MRI will be performed at 4 weeks after radiosurgery.

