12. CRITERIA FOR EVALUATION/REMOVAL FROM STUDY

Every subject should be encouraged to remain in the study. Possible reasons for early withdrawal may include, but are not limited to, the following:

1. Withdrawal of consent – Subject decides to withdraw from the study. This decision must be an “independent decision” that is documented in the source documentation
2. Principal Investigator and/or treating physician discretion – The Principal Investigator and/or treating physician may choose to withdraw a subject from the study if there are safety or other concerns.
3. Subject non-compliance.
4. Subject lost to follow-up.
5. Subject enrolled in hospice care.
6. Subject death.

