14.8 Analysis of Secondary Objectives

For the secondary objectives of 6-month local control, 6-month radiographic radiation necrosis, 12-month symptomatic radiation necrosis, 12-month local control, 12-month radiographic radiation necrosis and 12-month local control rate by SRS modality, Kaplan-Meier methods will be used to provide point estimate with 95% confidence intervals. The method of Klein et al., (Klein et.al., 2007) will be conducted for the group comparison.

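### The futility look in 14.4 does not fix which 20 patients are counted; if they are taken as outcomes become available, local failures are over-represented and the 75% test does not hold its level

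*Combined protocol and SAP*

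**What the plan says.** Section 14.4 (Sample Size) adds an interim analysis of local control to a 42-patient single-arm design. It is triggered "When 20 patients have been enrolled in the study with their local control outcome being available". The test is a "binomial exact test for the null hypothesis that the proposed method can maintain a 6 month local control rate of at least 75" per cent, and the consequence is stated plainly: "If p-value of this binomial test is less than 0.05, we will reject the null hypothesis and terminate this study earlier for futility".

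Four other places determine when a patient has such an outcome:

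- Section 4.2 counts as a failure any new, recurrent or progressing "tumor within the planning target volume compared to pre-SRS on any post-treatment MRI by 6 months".
- Section 8.5 schedules the first scan, "along with a brain MRI will be performed at 4 weeks after radiosurgery". Section 8.6 and the Study Calendar add scans at about months 3 and 6.
- Section 12 (Criteria for Evaluation/Removal from Study) lists reasons for leaving early, among them death, loss to follow-up, withdrawal of consent and "Subject enrolled in hospice care".
- Section 14.1 says that missing data are not imputed.

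For the later analysis of 6-month local control, section 14.8 says "Kaplan-Meier methods will be used to provide point estimate with 95% confidence intervals". Nothing comparable is said for the interim look.

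**The concern.** An exact binomial test assumes that the 20 patients were chosen without regard to their outcome. Section 14.4 does not secure this, for two reasons.

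1. **Timing.** A failing patient can have a known outcome one or three months after SRS; a controlled patient cannot have one before month 6. While accrual continues, a late enrollee who fails early can be counted before an earlier enrollee who is still controlled.
2. **Exits.** A patient who leaves while controlled has no 6-month result, and no rule says whether that patient counts.

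The stake is a wrong stop. The look can end the trial at about 20 outcomes, before the 40-patient primary analysis, when local control is in fact at or above the 75% limit.

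**Working it through.** **Reference: the rule as a plain binomial test.** The plan gives no boundary, so it has to be derived. With n = 20 and p0 = 0.75, P(X ≤ 11) = 0.041 and P(X ≤ 12) = 0.102, where X is the number controlled. A one-sided test at 0.05 therefore stops at 11 or fewer controlled. (The plan does not state sidedness; a two-sided test would stop at 10 or fewer.) At true control of 80%, the rate that section 2 attributes to standard dosing, P(X ≤ 11) = 0.010.

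**Why timing matters.** Assume a constant failure hazard and true 6-month control of 75%.

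- Failures seen at month 1: 1 − 0.75^(1/6) = 0.047.
- Failures seen at month 3: 0.75^(1/6) − 0.75^(1/2) = 0.953 − 0.866 = 0.087.
- Failures seen at month 6: 0.866 − 0.750 = 0.116.

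So 0.134 of the 0.250, just over half of all failures, are known at month 3 or earlier, when no controlled patient yet has a 6-month outcome.

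**Reading A: the 20 fill up in calendar order of availability.** Monte Carlo, 42 patients per trial, scans at months 1, 3 and 6, Poisson accrual, exits independent of failure, stop at 11 or fewer controlled. Accrual and exit rates are assumptions, because the documents give neither.

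| True control | Exit probability by month 6 | 1/month | 2/month | 4/month |
|---|---|---|---|---|
| 75% | 0% | 6% | 9% | 17% |
| 75% | 20% | 8% | 11% | 18% |
| 75% | 40% | 12% | 14% | 18% |
| 80% | 0% | 1.6% | 2.5% | 5.4% |

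The entries are probabilities of stopping; the nominal values are 4.1% at 75% and 1.0% at 80%. With 30% exits, the probability at 75% is about 10–19% over the same accrual rates. Mean observed control at true 75% is about 67–73%. Failure timing matters too: across mostly-late to mostly-early failures and 0–40% exits, the range at 75% is 5–26%.

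**Reading B: evaluable patients taken in enrolment order.** The timing effect disappears; only the loss of controlled leavers remains. With 30% exits at constant hazard:

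- Observed failures: 0.047 × 0.7^(1/6) + 0.087 × 0.7^(1/2) + 0.116 × 0.7 = 0.198.
- Observed controlled: 0.75 × 0.7 = 0.525.
- Apparent control: 0.525 / (0.525 + 0.198) = 0.726.
- P(X ≤ 11 | n = 20, p = 0.726) = 0.07.

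Over 0–30% exits the false-stop probability is about 4–8%.

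**A fixed set of the first 20 treated.**

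- With no exits the exact test applies, and the false stop is 4.1%.
- With exits, the Kaplan-Meier estimate averages 75%, but an uncalibrated one-sided log-log test runs at about 6.1–6.5% for 5–40% exits.
- Counting leavers as controlled errs the other way: the false stop falls to 1.7% at 20% exits and 0.5% at 40%, so the look loses its ability to stop.

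**The case against.** The strongest reply is that Reading A is not in the text. Section 14.4 does not say that the first 20 outcomes by calendar date are used. Its endpoint is the 6-month rate, so 20 patients each followed to month 6 is a natural reading, and the excess is then small. A reader might also infer that later enrollees silently replace those who leave. The documents do not say so: the only stated replacement (8.3) is for withdrawals at the planning scan, and 14.3 puts everyone who completed SRS in the efficacy population. This stands, and it makes the larger figures conditional on Reading A. It does not remove the gap, because 14.3 settles neither which 20 count nor how leavers count in a binomial test.

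Second, a reader might infer false-stop rates near 30%. Rates of that size at 30% exits or fewer arise if failures are known the instant they occur. The protocol detects them at scheduled scans, which gives the lower figures above. Section 11.2 slows declaration further: where treatment effect is suspected, standard MRI alone is not enough and a repeat scan generally follows within about 6 weeks. If every failure seen at month 1 or 3 took 1.5 months to confirm, the no-exit figures would fall to about 5%, 6% and 10.5% at 1, 2 and 4 patients per month. That delay is an upper bound, since not every failure needs confirmation.

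Third, the direction of the exit effect is assumed. If patients who die or enter hospice were about to fail, dropping them would shrink or reverse it. The timing effect does not depend on this.

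Finally, this is a futility look on a secondary endpoint in a pilot. Extra stopping does not inflate false success on symptomatic radiation necrosis. That stands and limits the severity.

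**Conclusion.** The point holds in conditional form. Section 14.4 leaves the interim set open, and the protocol's own outcome definition and scan schedule make failures known earlier than control. If the 20 are taken as outcomes become available, the test does not hold its level: about 6–17% false stops with no exits and 10–19% with 30% exits at true control of 75% (nominal 4.1%), and about 1.6–6% at true control of 80% (nominal 1.0%). These figures rest on constant hazards, scans at months 1, 3 and 6, exits independent of failure and accrual of 1 to 4 patients per month; confirmation delay would lower them. In enrolment order, the figure at 75% is about 4–8%, and the excess comes only from dropping controlled leavers. The documents do not show which set is intended, so they do not support a claim that the trial will be stopped wrongly at the higher rates. Severity: should be fixed.

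**What to change.** In 14.4:

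- Define the interim set as the first 20 treated Cohort 1 patients in order of SRS date.
- Take the decision only when each of them has failed, left, or had the 6-month scan.
- State that the test is one-sided. If all 20 are evaluable, keep the exact binomial test and state its boundary: stop at 11 or fewer controlled.
- If some leave while controlled, keep them in the set through the Kaplan-Meier estimate that 14.8 already uses, with a boundary calibrated to one-sided 5%. The calibration is needed because the uncalibrated log-log test runs at about 4–7%.

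The cost is a few sentences, a short simulation to set the boundary, and a look that may come slightly later. Some stopping at poor control is also lost. At true control of 57% (the rate that section 2 quotes for multi-agent ICI alone), the calendar-order rule stops in 66–94% of trials if failures are known at once, which overstates the figure for scheduled scans; the fixed set with the uncalibrated Kaplan-Meier test stops in 52–57%. That extra stopping came from the biased sample.

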2. BACKGROUND & RATIONALE

Epidemiology

Occurring ten times more frequently than primary brain tumors, brain metastases are by far the most common intracranial malignancy (Nabors et al., 2017). Associated with a median overall survival of 4-5 months, brain metastases afflict more than 200,000 people annually in the United States, comprising up to 30% of adults with cancer (Pruitt et al., 2017; Gibney et al., 2012; Fife et al., 2004; Davies et al., 2011).

Treatment of Brain Metastases

In general, treatment of metastatic brain disease involves surgical resection, whole brain radiation therapy (WBRT), stereotactic radiosurgery (SRS), and/or systemic therapy. While conventional systemic therapies alone are typically not sufficient to control intracranial disease due to the presence of the blood-brain barrier, newer studies suggest efficacy of immunotherapy – predominantly via immune checkpoint inhibitors (ICI). Recent Level I evidence in patients with metastatic melanoma indicates that the 6-month local control rate of brain metastases treated with multi-agent ICI alone (nivolumab + ipilimumab) is 57% (Tawbi et al., 2018), compared to the 24% rate of ipilimumab alone (Margolin et al., 2012), the 22% rate of pembrolizumab alone (Goldberg et al., 2016), or the 50% rate of ipilimumab + fotemustine (DiGiacomo et al., 2012). While the local control rate of multi-agent ICI is encouraging, it is important to remember that the 57% rate remains vastly inferior to the six-month local control rates of 87-91% achieved following single-fraction SRS administered via linear accelerator or Gamma Knife (Tawbi et al., 2018; Bernard et al., 2012; Minniti et al., 2017; Matsunaga et al., 2018). Candidates for SRS are typically patients with 1-10 brain metastases, while patients exceeding 10 brain metastases often receive WBRT instead of SRS (Yamamoto et al., 2014).

Morbidity of Standard-Dose Stereotactic Radiosurgery + Immunotherapy for Metastatic Brain Disease

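### The interim local-control rule in 14.4 waits for 20 complete 6-month outcomes, although a ninth local failure already settles the result

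*Combined protocol and SAP*

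**What the plan says.** Section 14.4 (Sample Size) adds one interim analysis of 6-month LC to a 42-patient single-arm design. It takes place "When 20 patients have been enrolled in the study with their local control outcome being available". The method is stated as "we will conduct a binomial exact test" of the "null hypothesis that the proposed method can maintain a 6 month local control rate of at least 75" per cent, and the action as "If p-value of this binomial test is less than 0.05, we will reject the null hypothesis and terminate this study earlier for futility".

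The section does not give the cut-off as a number of patients, the sidedness of the test, the chance of stopping at any true LC rate, an accrual rate, or whether enrolment pauses while outcomes mature.

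Four other places bear on the point:

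- Section 4.2 defines LC through new, recurrent or progressing tumour in the planning target volume on any scan after treatment up to 6 months. The study calendar puts scans at 1, 3 and 6 months in that period, each with a 30-day window either way.
- Section 2 gives 57% as the 6-month LC with multi-agent immune checkpoint inhibitors (ICI) alone and comments that "the 57% rate remains vastly inferior to the six-month local control rates of 87-91% achieved following single-fraction SRS". It states the efficacy hypothesis as non-inferiority "compared to the 80% local control rate associated with the RTOG 90-05-established SRS dosing parameters".
- Section 14.8 analyses overall LC by Kaplan-Meier estimates with 95% confidence intervals and plans no test against 75% or 80%.
- Section 17 provides for monthly team review that covers responses, and lets the investigators or the data and safety monitoring committee (DSMC) bring about early closure.

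**The concern.** The trial gives less than the standard radiosurgery dose, so loss of tumour control is the foreseeable price. The primary endpoint measures only necrosis, which leaves the interim test as the only prespecified decision rule for LC.

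The rule waits for information that it may not need. A local failure cannot be undone by later follow-up, and failures become visible on scans from month 1 onward. Once enough have been seen, the test result is known, yet as written the study carries on until 20 outcomes are complete. If accrual continues meanwhile, more patients receive a regimen that the plan's own criterion has already rejected. Because the cut-off and its stopping probabilities are not printed, an ethics board or DSMC member cannot see where the boundary lies or how sensitive it is.

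**Working it through.** **Inputs.** From 14.4: n = 20, null LC of at least 75%, exact binomial test, stop if p < 0.05, total sample size 42. From Section 2: 57% (ICI alone) and 80% (reference for standard dosing). The plan states no cut-off or stopping probability for the interim, so there is no figure to reproduce.

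**Cut-off.** A null of at least 75% can be rejected only by low counts, so the natural reading is one-sided. With X the number controlled, p = P(X ≤ x | n = 20, LC = 0.75):

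- x = 11: p = 0.0409, stop
- x = 12: p = 0.1018, continue

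The rule stops at X ≤ 11, an observed LC of 55% or less. An observed 12/20 (60%) continues. In failures F = 20 − X, the boundary is F ≥ 9.

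**Chance of stopping.** P(X ≤ k | n = 20, true LC):

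| True LC | k = 11 (rule as written) | k = 12 (for comparison) |
|---|---|---|
| 50% | 74.8% | 86.8% |
| 57% | 51.4% | 68.7% |
| 60% | 40.4% | 58.4% |
| 65% | 23.8% | 39.9% |
| 70% | 11.3% | 22.8% |
| 75% | 4.1% | 10.2% |
| 80% | 1.0% | 3.2% |

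A two-sided exact test would give p = 0.065 at 11/20. The cut-off would then be 10 and the chance of stopping at 57% would be 33.9%. The one-sided reading is therefore the one more favourable to the plan.

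**Why the result can be known early.** X ≤ 11 and F ≥ 9 are the same event when all 20 patients are evaluable. Under Section 4.2 a failure on any scan by 6 months counts, so F can only rise as follow-up proceeds. Once F = 9, no later outcome can bring X above 11. Stopping at the ninth failure therefore leaves every entry in the k = 11 column unchanged.

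**Cost of waiting.** The accrual rate is not given; let it be r per month without a pause. While the 20th patient reaches 6 months, min(22, 6r) more enrol: 6, 12 or 18 at r = 1, 2 or 3, for a total of 26, 32 or 38. All 22 are in at r = 22/6 ≈ 3.7, or at 22/7 ≈ 3.1 if the 30-day window is used in full.

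**Gain from stopping at the ninth failure.** Assume a true LC of 57% and failures first seen in equal shares at the 1-, 3- and 6-month scans. By simulation, in trials that stop, the decision comes about 5.5, 3.7 or 2.9 months earlier at r = 1, 2 or 3. About 20, 25 or 29 patients are then enrolled instead of 26, 32 or 38. Time needed to confirm a failure is not included.

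**Dependence on evaluability.** The equivalence needs 20 evaluable patients. If the count ran over a fixed first 20 of whom only 18, 16 or 14 were evaluable, P(F ≥ 9) at a true LC of 57% would fall to 36%, 21% or 9%.

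**The case against.** Several objections are fair and limit the point.

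- **Other safeguards.** A reader might infer that this rule is the only protection patients have. It is not: Section 17 has monthly review of responses and allows closure by the investigators or the DSMC. What stands is narrower: no other prespecified LC threshold guides those decisions.
- **The 57% benchmark.** That figure comes from ICI alone in melanoma, and Section 2 contrasts it with 87-91%, not with the 75% null. The interim was not designed to detect it. It remains a useful reference, since a true LC of 57% would mean that reduced-dose radiosurgery added nothing to that ICI-alone figure.
- **Early deaths.** Eligibility asks only for an estimated median survival of at least 6 months, so some patients will die before their outcome is known. A boundary tied to a fixed first 20 could weaken the rule, as the working shows. This stands in full, and the fix must count evaluable patients.
- **Confirmation takes time.** Section 11.2 calls for repeat scans or further testing when treatment effect is suspected. That shortens the gain by an unknown amount, but the ninth confirmed failure still cannot come later than complete outcomes with the same confirmation.
- **Accrual.** The plan is silent on a pause, and the enrolment figures rest on assumed rates. If enrolment did pause, early stopping would spare few patients.

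**Conclusion.** The point holds as a matter of timing and disclosure. The rule can be carried out, but it waits for complete outcomes that cannot alter a result already fixed by nine failures, and it prints neither its boundary nor its sensitivity. Its chance of stopping is 51% at a true LC of 57%, 40% at 60% and 24% at 65%. These figures follow from 20 patients, the 75% null and the 0.05 level; the delay does not cause them.

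Two stronger readings do not hold. A reader might infer that a poor regimen usually passes. That is true from about 60% upward, but at 57% the rule stops slightly more often than not, and at 50% it stops 75% of the time. A reader might also infer that the cut-off is wrong and should be 12. Nothing in the documents requires that. It would raise the chance of stopping at 57% to 69%, but would raise false stops from 4.1% to 10.2% at exactly 75% and from 1.0% to 3.2% at 80%. That is the sponsor's choice, not a correction.

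The conclusion assumes a one-sided test, one yes/no LC outcome per patient, and 20 evaluable patients. The plan does not say how several lesions combine into a patient's outcome or how early deaths count.

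**What to change.** In 14.4:

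1. State the boundary as 9 or more local failures among the first 20 LC-evaluable patients in enrolment order (one-sided exact test, p = 0.041). Define evaluable, and replace each non-evaluable patient by the next enrolled.
2. Trigger the stop as soon as the ninth failure is confirmed under the RANO-BM process in Section 11.2, without waiting for all 20 to reach 6 months.
3. Print the stopping probabilities (the k = 11 column above), and say whether enrolment pauses while outcomes mature.

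Statistically this costs nothing: every stopping probability stays the same, and a stop can only come earlier. The practical cost is an ongoing tally of confirmed failures and a short protocol amendment, which Section 16 sends to the ethics board. If the sponsor prefers a cut-off of 12 or fewer, the amendment should show both columns so that the higher false-stop risk is accepted openly.
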